7.4 Subsequent Timepoints

Timepoint 1

On completion of surgery and discharge from hospital

All study participants will be asked to complete the BREAST-Q questionnaire 2 weeks (+1 week) after having surgery. Patients will be due to be seen at a routine outpatient appointment and will be offered the opportunity to complete the questionnaires whilst in clinic. Due to COVID-19, the clinician and the patient may decide that a telephone clinic consultation is more appropriate rather than a face-to-face consultation. Participating in this study will not influence this decision making. For these cases where the follow up consultation is not face-to-face, a letter will be sent asking them to complete the questionnaire along with a pre-paid envelope to return the questionnaire.

Timepoint 2

All participants will be asked to complete the BREAST-Q questionnaire 3 months post-surgery (+ 6 weeks). Patients are routinely seen in a follow up clinic, so they will be offered the opportunity to complete the questionnaires whilst in clinic. If they are missed or if the clinic consultations are via telephone (as explained above), a letter will be sent to the participant asking them to complete the questionnaire booklet along with a pre-paid envelope to return the questionnaires.

Timepoint 3

All participants will be asked to complete the BREAST-Q questionnaire 12 months post-surgery (+ 6 weeks). Patients are routinely seen in a follow up clinic, so they will be offered the opportunity to complete the questionnaires whilst in clinic. If they are missed or if the clinic consultations are via telephone (as explained above), a letter will be sent to the participant asking them to complete the questionnaire booklet along with a pre-paid envelope to return the questionnaires.

7.5 Patient Outcome Measures (see appendix)

Participants in the study will complete the same measures on paper to ensure comparison between the timepoints. The questionnaire will be completed at baseline, 2 weeks and 3 and 12 months post-surgery.

7.6 Discontinuation/Withdrawal of Participants from Study

Each participant has the right to withdraw from the study at any time. In addition, the Investigator may discontinue a participant from the trial at any time if the Investigator considers it necessary for any reason including:

- Withdrawal of Consent
- If surgery not undertaken as planned at time of consent

Any data acquired prior to withdrawal will be included in the final analysis (unless consent is withdrawn by the participant). The reason for withdrawal will be recorded.

8 Statistics

As we are exploring patient perceived outcomes and not evaluating a new intervention, a power calculation is not required to calculate sample size. Based on the rate of immediate implant based reconstructions performed in the Leeds Breast and Reconstructive unit, we

estimate that approximately 60 patients will be available to complete the questionnaire per year. We have set a pragmatic target of 60 patients to be recruited over the study period. This is especially relevant given the current coronavirus pandemic which has had an impact on routine patient care during 2020.

8.1 Sample size and recruitment rate

This is a single centre study with a planned minimum sample size of 60 participants. We have allowed a 2 year period for recruitment.

8.2 General Considerations

Statistical analysis of the recruitment and attrition rates, data collection, measures and outcome data is the responsibility of the Chief Investigator (assisted by the study team). The questionnaire score for each participant will be converted into a Rasch scale (scores 0-100) as per BREAST-Q score conversion protocol. Simple comparative statistical analysis will be performed with the aid of SPSS to compare BREAST-Q scores between participants undergoing pre-pectoral implant reconstruction and sub-pectoral reconstruction. Each sub-module PROMs category within the BREAST-Q will also be directly compared between the two groups. The matched BREAST-Q scores over the four time periods for each participant will also be analysed to explore the potential change in scores over the study follow-up period. Patient outcome (e.g. complication rates, re-admission, additional cancer treatment) will also be correlated with the BREAST-Q scores to examine their potential impact on PROMs.

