We will collect PROMS on a prospective cohort of patients undergoing immediate implant based reconstruction after mastectomy for cancer or for risk reduction. The Association of Breast Surgery (ABS) guidelines for oncoplastic breast surgery [15] states that patients undergoing breast reconstruction should have PROMs data collected on a routine basis. We will utilise the BREAST-Q questionnaire (BREAST-Q, 2017), which is a validated PROMs survey that has been published widely.

5. Trial Design**5.1 Research Design**

A prospective non-randomised longitudinal cohort study with data collection for patients undergoing mastectomy with immediate implant based reconstruction surgery for early breast cancer or risk reduction using repeated measures and mixed methods.

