8.5 Patient Outcome Measures

Patient outcome measures will be summarised for each time point. Any differences between the two groups will be analysed where possible. All analyses will be used to help plan a future advice and information for patients undergoing implant based reconstruction.

9 Data Management

Data collection will occur in accordance with GCP, Caldicott principles and the General Data Protection Regulation (GDPR) 2018, and will work in line with NHS confidentiality guidelines and codes of conduct. All questionnaires will be fully anonymised and contain no patient identifiable details. Anonymised data will be manually inputted into an excel spreadsheet which will be held on a password protected location within a secure NHS departmental drive.

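### Section 8.2 explores change on matched scores over four time periods without technique; no technique-by-time comparison is stated, and the four periods mix two BREAST-Q modules

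*Protocol*

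**What the plan says.** Section 5.1 of the protocol describes the study as "A prospective non-randomised longitudinal cohort study with data collection" and says it uses repeated measures. Section 4 asks whether technique influences outcomes as patients perceive them, and all three objectives (aesthetics, pain, function) are comparisons of pre- with sub-pectoral reconstruction.

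Section 8.2 then sets out separate analyses:

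- Simple comparative statistics in SPSS to "compare BREAST-Q scores between participants undergoing pre-pectoral implant reconstruction and sub-pectoral reconstruction", with no time point named.
- The same by scale: "Each sub-module PROMs category within the BREAST-Q will also be directly compared between the two groups".
- Change over time: "The matched BREAST-Q scores over the four time periods for each participant will also be analysed to explore the potential change in scores". This sentence does not mention technique.

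Section 8.5 adds "Patient outcome measures will be summarised for each time point" and "Any differences between the two groups will be analysed where possible".

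On forms, Section 5.2 gives the Reconstruction Expectations module before surgery and the Reconstruction module afterwards, and ties the study of change to the latter. Section 7.5 says that participants complete the same measures so that time points can be compared. Section 7.3 has every patient complete the baseline form. For 3 and 12 months, Section 7.4 foresees missed clinics and telephone consultations: "If they are missed or if the clinic consultations are via telephone (as explained above), a letter will be sent to the participant". Section 7.6 states: "Any data acquired prior to withdrawal will be included in the final analysis (unless consent is withdrawn by the participant".

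**The concern.** The change analysis is the only place where the plan uses the repeated measurements within a woman, and as written it pools the two techniques. It can show that scores move after surgery. It cannot show whether they move differently after pre- and sub-pectoral reconstruction. Quicker recovery is one of the potential pre-pectoral advantages in Table 1, so that contrast bears on the study's question.

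Two further weaknesses sit in the same sentence:

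- **Missing forms.** Matched scores over several time points, analysed with simple methods, lead easily to paired or classical repeated-measures tests. These drop a woman who lacks any form in the set. In a cohort of about 60 this wastes data. It also biases the estimated change if women with low early scores return fewer later forms.
- **Scales.** Change over four periods requires the same scale at all four. On Section 5.2's description, the pre-surgery form is a different module.

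**Working it through.** The plan gives no power, effect size, SD, return rate or dropout rate, so it has no figure to reproduce. The check has three parts.

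**1. Where technique and time meet in the plan**

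| Section | Technique | Time |
|---|---|---|
| 8.2, comparison of scores and sub-modules | yes | not named |
| 8.2, matched scores | no | four periods |
| 8.5, summaries | not named | each time point |
| 8.5, group differences | yes, where possible | not named, but follows the per-visit summaries |

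Sections 8.2 and 8.5 together allow a technique comparison at each visit. Neither states a comparison of change by technique.

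**2. Which visits share a scale**

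Section 5.2: pre-surgery is Reconstruction Expectations; 2 weeks, 3 months and 12 months are Reconstruction. Only three of the four time points can yield a change score on one scale. Section 5.2 itself links change over time to the post-operative module, whereas Section 8.2 says four periods and Section 7.5 says the measures are the same. The three sections do not agree.

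**3. What a matched set could cost (illustration)**

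*Count.* Inputs: 60 women (Section 8.1); baseline form complete for all (Section 7.3); three later forms, each returned independently with an assumed probability r. Women with all forms = 60 × r³.

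| r | 60 × r³ | Lost |
|---|---|---|
| 0.95 | 51.4, about 51 | 14% |
| 0.90 | 43.7, about 44 | 27% |
| 0.85 | 36.8, about 37 | 39% |
| 0.80 | 30.7, about 31 | 49% |

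*Bias in change.* Assumptions: SD 20, within-woman correlation 0.6, true gain from 2 weeks to 12 months of 6.0 points, and the 2-week form always present. Each of the two later forms is returned with a log-odds that rises by 1 per SD of the 2-week score.

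Let s be the amount, in SD, by which the completers' mean 2-week score exceeds that of all women. Their 12-month mean is then raised by only 0.6 × s, so

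observed gain = 6.0 − (1 − 0.6) × 20 × s = 6.0 − 8s.

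Here s = E[z p(z)²] / E[p(z)²], where z is the standardised 2-week score and p(z) is the return probability, with the intercept set to give the stated average return.

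| Average return | Complete | s | Observed gain |
|---|---|---|---|
| 95% | 90% | 0.089 | 6.0 − 0.71 = 5.3 |
| 90% | 82% | 0.167 | 6.0 − 1.34 = 4.7 |
| 85% | 74% | 0.239 | 6.0 − 1.91 = 4.1 |
| 80% | 66% | 0.308 | 6.0 − 2.46 = 3.5 |

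At 85% return the gain among completers is about 4 points against a true 6.0. The completer share here is higher than 60 × r³ implies because only two forms can go missing and both depend on the same 2-week score.

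**The case against.** The strongest reply is that the text does not say what a critic might read into it.

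- *Women missing one form drop out.* A reader might infer this, but no complete-case rule is written. Matched scores for each participant can simply mean scores linked within a woman, and Section 7.6 keeps data collected before withdrawal. This stands: the loss is a risk of the wording, not a stated rule. Section 7.6 does not settle the matter, though, because it covers women who withdraw and not women who stay in but miss a form.
- *Recovery is never compared between techniques.* A reader might infer this too, and it goes too far. Sections 8.2 and 8.5 leave room for comparisons of pain and function at every post-operative visit, and none of the objectives asks for a difference in trajectory in so many words. Only the technique-by-time comparison is unstated.
- *The technique comparison is itself biased by matching.* Not supported: Section 8.2 does not restrict that comparison to matched sets.
- *Four missable forms.* Counting 60 × r⁴ would give 49, 39, 31 or 25 women, but Section 7.3 has every patient complete the baseline form.
- *This belongs in a SAP.* Model form and missing-data handling are commonly left there, and their absence is not the point. The point is that the protocol does specify a change analysis, leaves technique out of it, and spreads it over two modules.
- *Safeguards exist.* Section 7.4 posts a form with a pre-paid envelope, and Sections 8.3 and 9.3 report retention. These reduce and describe missingness; they do not say how the change analysis treats it.

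**Conclusion.** The point holds in a limited form. Section 8.2 analyses change separately from technique, and no section joins the two, although the design is longitudinal and every objective compares techniques. The four-period comparison also conflicts with Section 5.2, under which only the three post-operative visits share a module. Both conclusions rest on the text alone.

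The loss and bias from matching are conditional. They apply only if matching is carried out as a complete-set analysis, and their size rests on assumed return rates, SD, correlation and return mechanism. On those assumptions 14% to 49% of 60 women would be left out at 95% to 80% return, and a 6.0-point gain would appear as about 4 at 85% return. The plan is exploratory and unpowered, so this is an improvement worth making before analysis; it does not invalidate the study.

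**What to change.** In Section 8.2, replace the matched analysis with one linear mixed model per post-operative BREAST-Q scale:

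- **Terms:** technique, visit (2 weeks, 3 months, 12 months), technique-by-visit, and a within-woman covariance. SPSS, already named, fits this with its MIXED procedure.
- **Data:** every available score, whether or not the woman returned all forms.
- **Report:** the technique difference at each visit with its 95% confidence interval, and form completion by technique.
- **Sensitivity analysis:** the subset with all forms.

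Reconcile Sections 5.2, 7.5 and 8.2 on which module is given at which visit. If Section 5.2 is right, describe the Expectations module separately and confine change to the three post-operative visits.

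The cost is a few sentences and a little more analysis work. The model assumes that non-return depends only on observed data (missing at random). That cannot be verified, but it is weaker than what an unbiased complete-set analysis of change needs.

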6.2 Inclusion criteria

- Female age \geq 18 years
- Skin or nipple sparing mastectomy with immediate implant based reconstruction for cancer or for risk reduction (e.g. BRCA mutation)
- Unilateral or bilateral mastectomy
- Implant or expander based immediate reconstruction
- Able to read and understand questionnaire in English

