7.3 Baseline Assessments

Once written informed consent is obtained, participants will be asked to complete the baseline questionnaire. Clinical data will be obtained from medical notes by the clinician and/or research team and will include (but not limited to) gender, age, diagnostic details, co-morbidities, smoking status, previous surgical and planned treatments.

Timepoint 0

After consent but prior to surgery

Following written informed consent and prior to the planned surgery, the baseline BREAST-Q questionnaire will be completed by every patient.

The following data items will be collected during the study:

- Reason for surgery (cancer or risk reduction)
- Uni or Bilateral surgery
- Type of mastectomy (skin and nipple preserving or nipple sacrificing, skin reducing)
- Pre- or sub-pectoral reconstruction
- Any axillary surgery
- Breast implant size
- Details of any anaesthetic block used (to reduce post-operative pain)
- Any additional cancer treatments (e.g. chemotherapy, radiotherapy)
- Any complications (e.g. haematoma, infection)
- Unplanned hospital re-admission
- Unplanned further surgery
- Implant loss at 3 months due to infection
- Expectation of pain after surgery
- Expectation of appearance after surgery
- Expectation of breast symmetry
- Expectation of change in sensation
- Satisfaction of breast shape and implant
- Psychosocial well-being
- Physical well-being related to chest
- Satisfaction with the information and care provided by the clinical team
- Sociodemographic information

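### Protocol 8.2 relates additional cancer treatment to BREAST-Q without separating cancer from risk-reduction patients, so part of any score gap between indications could appear as a treatment association (minor)

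*Protocol*

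**What the plan says.** Protocol section 8.2 (General Considerations) first plans the main comparison between techniques: "Simple comparative statistical analysis will be performed with the aid of SPSS to compare BREAST-Q scores". It then adds a secondary analysis: "Patient outcome (e.g. complication rates, re-admission, additional cancer treatment) will also be correlated with the BREAST-Q scores to examine their potential impact on PROMs". For that analysis it names the exposure, a method (correlation) and a purpose (potential impact). It gives no analysis set, stratum or covariate, and section 8.5 adds none.

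Both indications are in one cohort. Section 5.1 describes "mastectomy with immediate implant based reconstruction surgery for early breast cancer or risk reduction using repeated measures and mixed methods", and section 6.2 admits "Skin or nipple sparing mastectomy with immediate implant based reconstruction for cancer or for risk reduction (e.g. BRCA mutation".

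The data items in section 7.3 include "Any additional cancer treatments (e.g. chemotherapy, radiotherapy" and, separately, "Reason for surgery (cancer or risk reduction". So the variable needed to tell the two indications apart is recorded, but nothing in section 8 uses it.

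On size, section 8.1 states: "This is a single centre study with a planned minimum sample size of 60 participants". Section 8 gives no effect size or standard deviation and says "a power calculation is not required to calculate sample size".

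**The concern.** Chemotherapy and radiotherapy as additional cancer treatment are things that happen to women with cancer. A woman having risk-reducing surgery would be expected to be coded as not treated, whatever her BREAST-Q score. The untreated group is then a mixture of cancer patients who needed no further treatment and women operated on for a different reason.

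If the two indications differ in BREAST-Q for any reason unrelated to chemotherapy or radiotherapy, such as age, expectations, the experience of a diagnosis or axillary surgery, some of that difference is attributed to treatment. Because 8.2 attaches the word impact to the result, and because sections 5.4 and 8.5 say the findings will feed into patient information, a reader could take an indication difference for a treatment consequence.

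**Working it through.** The protocol states no figure for this analysis, so there is none to reproduce. The check is whether, and by how much, indication can appear as treatment when treatment does nothing.

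**Inputs**
- N = 60: section 8.1, the planned minimum.
- r, share of women having risk reduction: not in the protocol; assumed 20% to 50%.
- t, share of cancer patients given additional treatment: not in the protocol; assumed 40% to 60%.
- G, mean score in risk-reduction women minus mean score in cancer patients: not in the protocol; size and sign unknown. G = 8 and G = 10 are used for illustration only.
- Standard deviation: not in the protocol; 20 points assumed where needed.
- True treatment effect: set to zero.
- All risk-reduction women coded untreated: an inference from the data items.

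**Formula.** Correlating a score with a yes/no variable amounts to comparing two means. The treated group contains cancer patients only. The untreated group has a share r of the cohort from risk reduction and a share (1-r)(1-t) from cancer. With no treatment effect:

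expected untreated minus treated difference = G × r / [r + (1-r)(1-t)]

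**Results for N = 60**

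| r | t | Risk reduction | Cancer, untreated | Cancer, treated | Fraction of G | G = 8 | G = 10 |
|---|---|---|---|---|---|---|---|
| 0.2 | 0.4 | 12 | 28.8 | 19.2 | 12/40.8 = 29% | 2.35 | 2.9 |
| 0.3 | 0.5 | 18 | 21 | 21 | 18/39 = 46% | 3.69 | 4.6 |
| 0.5 | 0.6 | 30 | 12 | 18 | 30/42 = 71% | 5.71 | 7.1 |

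The fraction depends only on r and t. The points scale directly with G, are zero if the indications score alike, and change sign with G.

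**Against sampling error.** In the middle row, with SD 20, the standard error of the treated-untreated difference is 20 × √(1/21 + 1/39) = 5.4 points. The spurious 3.7 points (G = 8) is about 0.7 of a standard error, and 4.6 points (G = 10) about 0.85. Over a wider grid (r 0.1 to 0.5, t 0.3 to 0.7, G = 10, SD 20) the chance of p < 0.05 with no treatment effect runs from about 6% to 30%, and is about 14% in the middle case, against a nominal 5%.

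**With restriction to cancer patients.** Both groups now have the same indication, so the indication component is zero. A simulation of 4,000 trials (r = 0.3, t = 0.5, G = 10, SD 20) gave a mean difference of about 4.8 points in the whole cohort (formula 4.6) and about 0.2 in cancer patients only (expected 0). The standard error rises from 5.4 to 20 × √(1/21 + 1/21) = 6.2 points.

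**The case against.** The strongest reply is that 8.2 does not say all participants are to be pooled. It is silent on the analysis set, and sets, subgroups and covariates for an exploratory correlation are commonly left to a statistical analysis plan, which may exist but is not shown. The reason for surgery is collected, so an analyst can restrict or stratify without new data. Treatment impact is not among the objectives in section 4, and the text speaks only of correlation and potential impact.

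Much of this stands, and it sets the severity. It does not dispose of the point. The protocol goes beyond silence: it names this exposure, this method and this purpose for a cohort that it defines as mixed. Followed as it most naturally reads, the analysis cannot separate treatment from indication.

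Several stronger readings might be inferred, and the documents do not support them:
- *That a false treatment effect will be reported.* Only part of any gap leaks in, the gap itself is unknown, and under the assumptions above the bias is less than one standard error in the middle case.
- *That risk-reduction women are untreated by definition.* Section 7.3 lists the two items separately and does not say how a woman with earlier cancer who has risk-reducing surgery is classified. The coding is a reasonable expectation, not a stated rule.
- *That technique differences distort the complication and re-admission correlations in the same way.* 8.2 names no adjustment for technique there, but nothing in the protocol allows the size of such an effect to be worked out. Models with several covariates would also be hard to support with about 60 women and the low complication rates that the background section describes.

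**Conclusion.** The point holds as a minor one. Section 8.2 sets out an analysis of additional cancer treatment that, if run on the whole cohort, partly confounds treatment with indication. About 29% to 71% of any cancer versus risk-reduction difference in BREAST-Q would appear as a treatment association, for assumed risk-reduction shares of 20-50% and treated shares of cancer patients of 40-60%. This rests on those assumed shares and on risk-reduction women being coded untreated. The size in points cannot be stated, because the protocol gives no basis for the gap or its direction.

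A reader might also infer that the pre- versus sub-pectoral comparison is compromised. This point does not show that: it concerns only the secondary correlation with additional treatment.

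**What to change.** Add one sentence to section 8.2: the analysis of additional cancer treatment against BREAST-Q scores will be limited to women whose recorded reason for surgery is cancer (or stratified by reason for surgery), and its result will be described as an exploratory association.

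No new data are needed. The cost is a smaller n for this one analysis: 60 × (1-r), which is 48, 42 or 30 women for assumed r of 20%, 30% or 50%. Little is lost, since women expected to be coded untreated throughout provide no treated-versus-untreated contrast of their own. Restriction removes only the indication component. Treated and untreated cancer patients may still differ in other ways, which is why the wording should stay at association.
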